## EXPERIMENTAL DESIGN SCHEMA

Treatment Schedule Table	
Days 1-28	4.7 mg/m  erdafitinib once daily, with maximum of 8 mg per day
Day 28	Evaluation

Erdafitinib will be administered orally once a day on a continuous basis; a cycle will be 28 days. Evaluations will occur at the end every other cycle x 3, then every 3 cycles.

Therapy will be discontinued if there is evidence of progressive disease or drug related dose-limiting toxicity that requires removal from therapy ([Section 6.0](#)). Therapy may otherwise continue for up to 2 years provided the patient meets the criteria for starting subsequent cycles ([Section 5.2](#)) and does not meet any of the criteria for removal from protocol therapy criteria ([Section 10.0](#)).

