## 5.0 TREATMENT PROGRAM

### 5.1 Overview of Treatment Plan

Treatment Schedule Table	
Days 1-28	4.7 mg/m  erdafitinib once daily, with maximum of 8 mg per day
Day 28	Evaluation

Erdafitinib tablets will be given orally once daily. A cycle of therapy is considered to be 28 days. A cycle may be repeated up to a total duration of therapy of 2 years (maximum 26 cycles). **On Day 1 of Cycle 2, the dose of erdafitinib should be held until a pre-dose plasma sample can be obtained. In order to obtain the 24-hour time point, the dose on Day 2, Cycle 2 should also be held until plasma sample is obtained.**

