**8.0 EVALUATIONS/MATERIAL AND DATA TO BE ACCESSIONED**

**8.1 Required Clinical, Laboratory and Disease Evaluation**

All clinical and laboratory studies to determine eligibility must be performed within 7 days prior to enrollment unless otherwise indicated. Laboratory values used to assess eligibility (see [Section 4.0](#)) must be no older than seven (7) days at the start of therapy. Laboratory tests need **not** be repeated if therapy starts **within** seven (7) days of obtaining labs to assess eligibility. If a post-enrollment lab value is outside the limits of eligibility, or laboratory values are older than 7 days, then the following laboratory evaluations must be re-checked within 48 hours prior to initiating therapy: CBC with differential, bilirubin, ALT (SGPT) and serum creatinine. If the recheck is outside the limits of eligibility, the patient may not receive protocol therapy and will be considered off protocol therapy. Imaging studies, bone marrow aspirate and/or biopsy, must be obtained within 14 days prior to start of protocol therapy (repeat the tumor imaging if necessary).

STUDIES TO BE OBTAINED	Pre-Study	During Cycle 1	Prior to Subsequent Cycles^
History	X	Weekly	X
Physical Exam with vital signs	X	Weekly	X
Neurologic Exam	X		
Height, weight, BSA	X		X
Performance Status	X		
Pregnancy Test 	X		
CBC, differential, platelets	X	Twice Weekly (every 3 to 4 days) 	Weekly 
Urinalysis	X		
Electrolytes including Ca ++ , PO 4 , Mg ++	X	Weekly	X
Creatinine, ALT, bilirubin	X	Weekly	X
Albumin	X		X
Tumor Disease Evaluation 4-A, 4-B,	X		Every other cycle x 3 then q 3 cycles 
Bone Marrow Aspirate and/or biopsy 	X 		
EKG	X		
Ophthalmologic exam 	X	X	Every cycle during the first 4 cycles of treatment, then every 3 cycles afterward 
Plain radiograph tibial growth plate (Bone X-Ray Tests) 	X		Prior to cycles 2, 5 and every 6 months
Medication Diary 		Weekly	X
Pharmacokinetics (optional) 			
Circulating Tumor DNA (ctDNA- optional) 			Cycle 5, Day 1 and (for patients receiving ≥ 5 cycles

			only) at end of Protocol Therapy OR disease progression
--	--	--	---

- ^ Studies may be obtained within 72 hours prior to the start of the subsequent cycle.

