- 1 Women of childbearing potential require a negative pregnancy test prior to starting treatment; sexually active patients must use an acceptable method of birth control. Abstinence is an acceptable method of birth control.
- 2 If patients have Grade 4 neutropenia then CBCs should be checked at least every other day until recovery to Grade 3 or until meeting the criteria for dose limiting toxicity.
- 3 If patients develop Grade 3 or greater thrombocytopenia then CBCs should be checked every 3 to 4 days until recovery per [Section 6.1](#).
- 4 Tumor Disease Evaluation should be obtained on the next consecutive cycle after initial documentation of either a PR or CR. Subsequent scans may restart 2 cycles after the confirmatory scan. If the institutional investigator determines that the patient has progressed based on clinical or laboratory evidence, he/she may opt not to confirm this finding radiographically.
- 4-A Neurological exam is also required for CNS patients.
- 4-B Non-Hodgkin Lymphoma/ Histiocytosis patients are required to have PET scans within 2 weeks prior to start of therapy and should also be followed with PET scans if positive at diagnosis. Refer to [Section 12.8](#).
- 4-C Patients with neuroblastoma must have both CT/MRI and MIBG scintigraphy prior to the start of therapy if the patient was enrolled with or has a history of having MIBG avid tumor. Otherwise the patient must have both CT/MRI and bone scan prior to the start of therapy. For patients with neuroblastoma and measurable disease by CT or MRI, lesions should be measured and followed using the same modality (CT or MRI) in addition to MIBG or bone scan. For patients with neuroblastoma and evaluable disease by MIBG scintigraphy or bone scan, use the same modality (MIBG scintigraphy or bone scan) to image and follow patients; CT/MRI are not required but may be performed as clinically indicated. Refer to [Section 12.5.4](#) and [Section 12.9](#).
- 5 Bone marrow aspirate and/or biopsy only required in patients suspected of having bone marrow metastasis on the basis of history, symptoms, laboratory evaluation or other clinical data.
- 6 Bone marrow aspirate and/or biopsy should be performed only when complete response or partial response is identified in target disease or when progression in bone marrow is suspected.
- 7 Medication diary (see [Appendix III](#)) should be reviewed weekly during cycle 1, after completion of each treatment cycle and uploaded into RAVE.

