#### 11.3.2 **Histology-Specific Biomarker Positive Expansion Cohorts:**

If ≥ 3 patients in the primary cohort with the same histology show signs of objective response (CR/PR according to the response criteria in [Section 12.3](#)), a histology-specific biomarker positive expansion cohort will open after the primary cohort is completed to up to 7 evaluable patients for a total sample size of 10 evaluable biomarker positive patients with that histology. This will allow us to estimate more precisely the activity in biomarker positive patients of that histology. See [Appendix VII](#) for a list of target tumor histologies.

We will open up to 3 such expansion cohorts for biomarker positive patients (i.e., if 3 histologies have ≥ 3 responses, we will open a total of 3 expansion cohorts as described above). Note that this can only happen if the response rate in the primary cohort is at least 45% (9/20) and there cannot be more than 21 additional evaluable patients in total for these expansion cohorts.

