#### 11.5 **Evaluability for Response**

Any eligible patient who is enrolled and receives at least one dose of protocol therapy will be considered evaluable for response. Any patient who receives non-protocol anti-cancer therapy during the response evaluation period will be considered a non-responder for the purposes of the statistical rule, unless they show an objective response prior to receiving the non-protocol anti-cancer therapy (in which case they will be considered a responder). Patients who demonstrate a complete or partial response confirmed by central review will be considered to have experienced a response. When opening expansion cohorts, the evaluation period for determination of best response will be the first 6 treatment cycles. All other patients will be considered non-responders. Patients who are not evaluable for response evaluation may be replaced for the purposes of the statistical rule. All patients considered to have a response (CR or PR) must have imaging studies reviewed centrally at the COG. Centers will be notified by the COG about requests for scans of patients with stable disease. Preliminary assessment of activity using institutionally provided tumor measurements will be entered into CDUS quarterly. The central review by COG will be provided as the final reviewed assessment of response when such becomes available.

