### 12.3 Response Criteria for Patients with Solid Tumors

See the table in [Section 8.0](#) for the schedule of tumor evaluations. In addition to the scheduled scans, a confirmatory scan should be obtained on the next consecutive cycle following initial documentation of objective response.

As outlined, patients will be assigned to one of the following categories for assessment of response: a) solid tumor (non-CNS) and measurable disease ([Section 12.4](#)); b) neuroblastoma with MIBG positive lesions ([Section 12.5](#)); c) CNS tumor ([Section 12.7](#)); and d) non-Hodgkin lymphoma/histiocytosis ([Section 12.8](#)). Note: Neuroblastoma patients who do not have MIBG positive lesions should be assessed for response as solid tumor patients with measurable disease.

Response and progression will be evaluated in this study using the revised Response Evaluation Criteria in Solid Tumors (RECIST) guideline (version 1.1) [*Eur J Ca* 45:228-247, 2009]. Key points are that 5 target lesions are identified and that changes in the *largest* diameter (unidimensional measurement) of the tumor lesions but the *shortest* diameter of malignant lymph nodes are used in the RECIST v 1.1 criteria.

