**12.9 Best Response**

Two objective status determinations of disease status, obtained on two consecutive determinations, separated by at least a 3 week time period, are required to determine the patient's overall best response. Two objective status determinations of CR before progression are required for best response of CR. Two determinations of PR or better before progression, but not qualifying for a CR, are required for a best response of PR. Two determinations of stable/no response or better before progression, but not qualifying as CR or PR, are required for a best response of stable/no response; if the first objective status is unknown, only one such determination is required. Patients with an objective status of progression on or before the second evaluations (the first evaluation is the first radiographic evaluation after treatment has been administered) will have a best response of progressive disease. Best response is unknown if the patient does not qualify for a best response of progressive disease and if all objective statuses after the first determination and before progression are unknown.

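### Read literally, the 6-cycle window for opening expansion cohorts leaves out a response first documented at the end-of-cycle-6 scan, because its confirmation is due in cycle 7

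*Combined protocol and SAP*

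**What the plan says.** Section 11.3.2 opens an expansion cohort for a histology in which at least 3 primary-cohort patients respond, and places this late in the trial: "a histology-specific biomarker positive expansion cohort will open after the primary cohort is completed". Section 11.5 sets the period for judging those responses: "When opening expansion cohorts, the evaluation period for determination of best response will be the first 6 treatment cycles".

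Four other parts of the protocol decide what fits into that period.

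- Cycle length (5.1): "A cycle of therapy is considered to be 28 days".
- Scan schedule (Experimental Design Schema): "Evaluations will occur at the end every other cycle x 3, then every 3 cycles". The table in 8.1 agrees: "Every other cycle x 3 then q 3 cycles".
- Confirmatory scan (8.1, footnote 4): "Tumor Disease Evaluation should be obtained on the next consecutive cycle after initial documentation of either a PR or CR". Section 12.3 repeats this: "a confirmatory scan should be obtained on the next consecutive cycle following initial documentation of objective response".
- Best response (12.9): "Two determinations of PR or better before progression, but not qualifying for a CR, are required for a best response of PR". The two determinations must be at least 3 weeks apart; Table 1 in 12.4.3 asks for 28 days. A CR likewise needs two determinations.

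Section 11.4 defines a responder by a best response of PR or CR on the study, with no cycle limit.

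**The concern.** The window in 11.5 applies to determining best response, and best response is a defined term that needs two determinations. Three scheduled evaluations fall inside the window, but a response that first appears at the third has its confirmatory scan outside it. Taken at its word, the plan then treats a patient whose response began inside the stated period, and was later confirmed, as not having responded for the expansion decision. The same patient is a responder for the primary endpoint.

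At stake is whether a histology reaches its count of 3. With so low a count in a 20-patient cohort of mixed histologies, reclassifying one patient can decide whether a cohort opens.

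**Working it through.** **The plan's own figures.** The primary rule is at least 3 responses in 20, for 5% against 25% (11.3.1). By exact binomial, P(X ≥ 3 | 20, 0.05) = 0.0755 and P(X ≥ 3 | 20, 0.25) = 0.9087. The stated 10% and 90% are consistent with this, with 10% as the ceiling and not the attained level. This rule uses 11.4's on-study definition, so the window does not enter it.

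**Dates.** With 28-day cycles and no delays, the window closes on day 6 × 28 = 168.

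| First documented | Day | Confirmatory scan | Day | Inside window? |
|---|---|---|---|---|
| End of cycle 2 | 56 | End of cycle 3 | 84 | Yes |
| End of cycle 4 | 112 | End of cycle 5 | 140 | Yes |
| End of cycle 6 | 168 | End of cycle 7 | 196 | No, 28 days late |

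An earlier second scan does not rescue the last row. Under the 3-week minimum in 12.9 the earliest date is 168 + 21 = day 189. If the cycle 6 scan is taken 72 hours early, as 8.1 permits, it is 165 + 21 = day 186. These are 21 and 18 days after the window closes.

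**Status of such a patient.** Take stable disease at cycles 2 and 4, then a first PR at cycle 6. By day 168 there is one determination of PR, and 12.9 needs two. Section 12.9.1 says that the assignment depends on confirmation as well as measurement, and its Table 5 leaves a PR or CR with no following assessment unclassifiable. So there is no best response of PR within the window. Under 11.4 the cycle 7 scan makes the patient a responder on study.

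**Illustration of size.** The documents give no data on when responses appear, nor how many patients will share a histology. Assume n = 6 of one histology, a true confirmed response rate p, and a share f of responders first seen at cycle 6. With q = p(1 − f),

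P(X ≥ 3) = 1 − Σ (k = 0 to 2) C(6, k) q^k (1 − q)^(6 − k).

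For p = 0.25 and f = 0 this is 1 − (0.1780 + 0.3560 + 0.2966) = 0.169. For f = 20%, q = 0.20 and it is 1 − (0.2621 + 0.3932 + 0.2458) = 0.099.

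| p | f = 0 | f = 10% | f = 20% | f = 33% |
|---|---|---|---|---|
| 0.25 (the design alternative) | 0.17 | 0.13 | 0.10 | 0.06 |
| 0.50 | 0.66 | 0.56 | 0.46 | 0.32 |

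The value f = 33% is simply one scan in three. Nothing in the documents favours any of these shares.

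**The case against.** The strongest reply is that the plan does not expressly require confirmation inside the window. Section 11.3.2 words the trigger as patients who show signs of an objective response under 12.3, and 12.3 separates first documentation from the later confirmatory scan. On that reading a first PR at the end of cycle 6 is enough. This stands as a possible reading, but it does not remove the problem. Section 11.5 speaks of best response, and 12.3 itself calls for the confirmatory scan. The two sections can therefore give opposite answers for one patient.

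Three stronger readings are tempting, and the documents do not support them.

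- A reader might infer that the cycle 6 scan can never yield a responder. It can, as the second determination: PR at cycle 4, the cycle 5 scan missed, PR again at cycle 6. A response first seen on an off-schedule cycle 5 scan can also be confirmed at cycle 6. Only a response first seen at cycle 6 is affected.
- A reader might take the next sentence of 11.5, which makes all other patients non-responders, as aimed at anyone outside the window. Section 12.3.1.1 has the same default with no window, set against responders confirmed by central review. That is the likelier contrast in 11.5 too, and confirmation there means central review, not a second scan. The exclusion rests on 11.5 read with 12.9, not on that sentence.
- A reader might infer a bias against slowly responding histologies. Without response-timing data this cannot be shown.

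It is also fair to say that any fixed window makes some on-study responders ineligible for the decision. A response first seen at cycle 9 would still be left out after the fix. What is particular here is that a response first seen inside the stated period is left out.

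**Conclusion.** The concern holds in a limited form. On the literal text, a CR or PR first documented at the scheduled end-of-cycle-6 evaluation cannot become a best response within 6 cycles, and so does not count towards the 3 responders of one histology. The dates follow from the protocol alone, assuming no cycle delays. That confirmation must fall inside the window is the natural reading of 11.5 with 12.9, but it is not certain that the sponsor intends it.

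Only the decision to open an expansion cohort is affected. One might suppose that the primary test loses power. It does not, because 11.5 ties the window to opening expansion cohorts; the 3-of-20 rule, its alpha and power, and the final response rate are untouched. The expansion cohorts serve estimation and carry no further test.

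The size of the effect is unknown. Under the assumed shares of 10% to 33% with six patients of one histology, the absolute loss in the chance of reaching 3 is about 4 to 11 points at a 25% response rate and about 10 to 34 points at 50%. The larger losses require a response rate twice the design alternative. The case for acting is that the stated rule discards a confirmed response and that the repair is cheap.

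**What to change.** Replace the window sentence in 11.5 with wording such as:

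> For the decision to open an expansion cohort, a patient counts as a responder if CR or PR is first documented at or before the end-of-cycle-6 evaluation, is confirmed on the confirmatory scan required on the next consecutive cycle (Section 8.1, footnote 4), even if that scan falls in cycle 7, and is confirmed by central review.

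Then change 11.3.2 so that its trigger refers to this definition.

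The wording names the confirmatory scan on purpose, because a phrase such as the next scheduled evaluation could be taken to mean the regular scan at the end of cycle 9. It also keeps the central-review condition already in 11.5. If the cycle 7 scan is missed, this wording does not count the response. Accepting the cycle 9 scan instead would mean a wait of 3 × 28 = 84 days after cycle 6, and the sponsor should say so if that is wanted.

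The cost is two small text changes and no extra scan, since footnote 4 already requires the one in cycle 7. The expansion decision may wait about 4 weeks for a patient with an unconfirmed response at cycle 6. In practice that concerns only the last patients enrolled: without delays, anyone who started at least 28 days before the last patient reaches day 196 by the time the last patient reaches day 168. The primary cohort is expected to take 2.7 to 6 years (11.1), so the delay is minor.

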#### 11.6 **Evaluability for Toxicity**

All eligible patients who receive at least one dose of protocol therapy will be considered in the evaluation of toxicity.

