### 1.2 Secondary Aims

- 1.2.1 To estimate the progression free survival in pediatric patients treated with erdafitinib with advanced solid tumors (including CNS tumors), non-Hodgkin lymphomas or histiocytic disorders that harbor genetic alterations in the *FGFR1/2/3/4*.
- 1.2.2 To obtain information about the tolerability of erdafitinib in children with relapsed or refractory cancer.
- 1.2.3 To provide preliminary estimates of the pharmacokinetics of erdafitinib in children with relapsed or refractory cancer.

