### 3.4 **Eligibility Checklist**

Before the patient can be enrolled, the responsible institutional investigator must sign and date the completed eligibility checklist. A signed copy of the checklist will be uploaded into RAVE immediately following enrollment.

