## 4.0 PATIENT ELIGIBILITY

All clinical and laboratory studies to determine eligibility must be performed within 7 days prior to enrollment unless otherwise indicated. Laboratory values used to assess eligibility must be no older than seven (7) days at the start of therapy. Laboratory tests need **not** be repeated if therapy starts **within** seven (7) days of obtaining labs to assess eligibility. If a post-enrollment lab value is outside the limits of eligibility, or laboratory values are older than 7 days, then the following laboratory evaluations must be re-checked within 48 hours prior to initiating therapy: CBC with differential, bilirubin, ALT (SGPT) and serum creatinine. If the recheck is outside the limits of eligibility, the patient may not receive protocol therapy and will be considered off protocol therapy. Imaging studies, bone marrow biopsy and/or aspirate (when applicable) must be obtained within 14 days prior to start of protocol therapy (repeat the tumor imaging if necessary).

Clarification in timing when counting days: As an example, please note that if the patient's last day of prior therapy is September 1st, and the protocol requires waiting at least 7 days for that type of

prior therapy, then that patient cannot be enrolled until September 8th.

**Important note: The eligibility criteria listed below are interpreted literally and cannot be waived. All clinical and laboratory data required for determining eligibility of a patient enrolled on this trial must be available in the patient's medical or research record which will serve as the source document for verification at the time of audit.**

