#### 11.4 **Methods of Analysis**

Response criteria are described in [Section 12](#). A responder is defined as a patient who achieves a best response of PR or CR on the study. Response rates will be calculated as the percent of evaluable patients who are responders, and confidence intervals will be constructed using the Wilson score interval method. Decision making for A'Hern design cohorts will follow rules described above.

Toxicity tables will be constructed to summarize the observed incidence by type of toxicity and grade. A patient will be counted only once for a given toxicity for the worst grade of that toxicity reported for that patient. Toxicity information recorded will include the type, severity, time of onset, time of resolution, and the probable association with the study regimen.

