### 14.2 CDUS

This study will be monitored by the Clinical Data Update System (CDUS) version 3.0. Cumulative protocol- and patient-specific CDUS data will be submitted quarterly to CTEP by electronic means. Reports are due January 31, April 30, July 31 and October 31. This is not a responsibility of institutions participating in this trial.

**Note: This study has been assigned to CDUS-Complete reporting, all adverse events (both routine and expedited) that have occurred on the study and meet the mandatory CDUS reporting guidelines must be reported via the monitoring method identified above.**

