##### 14.4.2 Monitoring by the Study Chair and MATCH Leadership

The study chair will monitor the study regularly and enter evaluations of patients' eligibility, evaluability, and dose limiting toxicities into the study database. In addition, study data and the study chair's evaluations will be reviewed by the MATCH Chair, Vice Chair and Statistician on a weekly conference call.

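### Section 11.6 limits the toxicity evaluation to eligible patients, so a dosed child later found ineligible would drop out of the toxicity tables

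*Combined protocol and SAP*

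**What the plan says.** The toxicity population is set in Section 11.6: "All eligible patients who receive at least one dose of protocol therapy will be considered in the evaluation of toxicity". The response population in Section 11.5 has nearly the same form: "Any eligible patient who is enrolled and receives at least one dose of protocol therapy will be considered evaluable for response".

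Section 11.4 describes the output: "Toxicity tables will be constructed to summarize the observed incidence by type of toxicity and grade". It adds that each patient counts once per toxicity, at the worst grade. It gives no denominator of its own.

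The tables serve secondary aim 1.2.2: "To obtain information about the tolerability of erdafitinib in children with relapsed or refractory cancer". Section 11.2 states that there are no pediatric phase 1 data for the drug, and Section 2.3.1 records no earlier experience in children.

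Several places bear on whether a dosed patient can be ineligible:

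- Section 3.5 declares ineligible any patient whose protocol therapy began before enrollment.
- Section 4.0 says that the criteria cannot be waived. The supporting data must be in the medical or research record, "which will serve as the source document for verification at the time of audit".
- Section 14.4.2 has the study chair enter evaluations of patients' "eligibility, evaluability, and dose limiting toxicities into the study database" while monitoring the study.
- Section 3.4 works the other way. Before enrollment, "the responsible institutional investigator must sign and date the completed eligibility checklist".

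**The concern.** An eligibility condition suits an activity estimate, because the response rate is meant to describe the target population. A safety table answers a different question: what happened to the children who took the drug. A child found after dosing to have breached a criterion was exposed all the same.

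The omission may also not be neutral. Many of the criteria are safety criteria: organ function and QTc interval in Section 4.1.7, interacting drugs in Section 4.2.2, eye conditions in Section 4.2.9. A child who was dosed despite breaching one of these could be informative about tolerability.

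At stake is how complete the descriptive tables are for aim 1.2.2. With so few patients, one omission can decide whether a toxicity appears in the tables at all.

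**Working it through.** **Step 1. Which population do the tables use?** Section 11.6 requires eligibility and at least one dose. Section 11.4 states no alternative, and no other section supplied defines an all-treated or safety set. The one other limit on toxicity evaluability is in Section 4.1.7.1.b: patients with known marrow metastatic disease are not evaluable for hematologic toxicity. That limit follows from the patients' disease. Section 11.6 gives no reason for its eligibility condition.

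**Step 2. Can a patient be dosed and ineligible?** Yes. Section 3.5 creates one such case by rule, and Sections 4.0 and 14.4.2 leave room for others to be identified after treatment starts.

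**Step 3. How many could there be?** The documents give no ineligibility rate. The planning figures of Sections 11.1 and 11.3.2 give only a loose frame:

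- Largest evaluable total: 20 + 3 × 7 = 41.
- Inflated for 15% inevaluability: 41 / 0.85 = 48.2, rounded up to 49. This reproduces the stated maximum.
- Allowance: 49 − 41 = 8 patients. Under Section 11.5 every eligible dosed patient is evaluable for response, so these 8 would be patients who were ineligible or never dosed. The split is not given. Dosed but ineligible patients could take up anything from 0 to 8 of that allowance.

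**Step 4. What would one omitted patient change?** No interval is planned for toxicity. For illustration I use the 90% Wilson interval that Section 11.3 applies to response. With x events in n patients and z = 1.645 (z² = 2.706), the limits are

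[x + z²/2 ± z·√(x(n − x)/n + z²/4)] / (n + z²).

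For x = 0 the upper limit reduces to z²/(n + z²).

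Check against the plan: 3/10 gives (4.353 ± 1.645 × √(2.1 + 0.676)) / 12.706 = 12.7% to 55.8%, which matches the 13% to 56% in the Section 11.3 table.

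Now assume one treated patient is later found ineligible. The first row for each cohort is the table under Section 11.6 when no eligible patient has the event. The other two rows count the extra patient.

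| Setting | x/n | Rate | 90% Wilson interval |
|---|---|---|---|
| Primary cohort, eligible only | 0/20 | 0% | 0 to 2.706/22.706 = 11.9% |
| Primary cohort, all treated, extra patient has the event | 1/21 | 4.8% | 1.1% to 18.8% |
| Primary cohort, all treated, no event | 0/21 | 0% | 0 to 2.706/23.706 = 11.4% |
| Largest total, eligible only | 0/41 | 0% | 0 to 2.706/43.706 = 6.2% |
| Largest total, all treated, extra patient has the event | 1/42 | 2.4% | 0.5% to 10.0% |
| Largest total, all treated, no event | 0/42 | 0% | 0 to 2.706/44.706 = 6.1% |

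**Step 5. More than one such patient (assumed).** Beside 20 eligible patients, 1, 2 or 3 dosed but ineligible patients make up 1/21 = 4.8%, 2/22 = 9.1% or 3/23 = 13.0% of all treated. A toxicity shown as 0/20 could be as high as those same fractions among all treated.

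**Step 6. Does the design move?** No. The sample size, the rule of at least 3 responses in 20, and its alpha and power all refer to the response set.

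**The case against.** The strongest reply is that exclusion is inferred. Section 11.6 says that eligible treated patients will be considered; it does not say that only they will be. Section 11.4 neither cites 11.6 nor uses the word eligible, so an all-treated table would not breach the text. This is correct, but it leaves an ambiguity at best. In a section headed as evaluability for toxicity, a stated condition is naturally read as the condition for being counted.

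Second, the events are not lost. Expedited reporting under Section 13 is not confined to eligible patients. Section 14.2 requires reporting of "all adverse events (both routine and expedited) that have occurred on the study" that meet the CDUS guidelines. The DSMC reviews results at least every 6 months (Section 14.4.1). This stands, and it limits the consequence. It does not settle the matter, because these are reporting and oversight rules and do not set the population for the tables.

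Third, such patients should be rare. There is a signed checklist before enrollment, and Section 4.0 requires a laboratory recheck before dosing in stated circumstances. Drug is ordered only after enrollment, without starter supplies or commercial stock, which makes the Section 3.5 case unlikely. This also stands. Sections 4.0 and 14.4.2 do not say that a dosed patient is reclassified, or when; they only leave room for it.

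Finally, APEC1621SC might define a safety set. It was not supplied, so the gap is shown only for the documents at hand.

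**Conclusion.** The concern holds, as a minor point. The only definition of the toxicity population in the supplied documents makes eligibility a condition. Applied as written, it leaves an exposed child who is later found ineligible out of the tables for aim 1.2.2.

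The effect is confined to those tables. Each omitted patient lowers every row's denominator by one, and lowers the numerator only for toxicities that patient had. The 0/20 against 1/21 contrast assumes that one such patient exists and is the only one with the event. If that patient has no event, the upper limit differs by only 0.5 points in the primary cohort and 0.1 points at the largest total. The actual count may be zero.

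No toxicity threshold, test or stopping rule in Section 11 depends on the tables, and reporting of individual events is unaffected.

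**What to change.** Reword Section 11.6 along these lines: *The toxicity evaluation includes every patient given one or more doses of protocol therapy, whether or not the patient is found to be eligible; patients found ineligible are flagged in the tables.* Keep the eligibility condition in Section 11.5 for response. The hematologic limit in Section 4.1.7.1.b is a separate, more specific rule and stands beside the new sentence as it does beside the present one; a cross-reference would make that plain.

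The cost is one sentence. The adverse events are already collected and reported, so no new data are needed. The small downside is that the tables may include a few patients outside the target population, which the flag makes visible. The response analysis and the 3/20 rule do not change. If the intention is already to tabulate all treated patients, the sentence simply says so.
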